#### 9.4.2 Analysis of Key Secondary Efficacy Endpoints

The key secondary efficacy endpoints include:

1. Change from baseline in QMG score at Week 26 in the overall study population.
2. Change from baseline in MG-ADL score at Week 26 in the AChR-Ab+ population.
3. Change from baseline in QMG score at Week 26 in the AChR-Ab+ population.
4. Change from baseline in MG-ADL score at Week 26 in the MuSK-Ab+ population.
5. Change from baseline in QMG score at Week 26 in the MuSK-Ab+ population.

The primary estimand of the changes from baseline is defined as follows:

- Population: Subjects in the FAS.
- Variable (endpoint): Change from baseline at Week 26.
- Intercurrent events:
  - Rescue therapy initiated after Day 28 during the RCP will be analyzed using a composite strategy. The data collected on or after the initiation of the rescue therapy will be imputed using the subject's worst observation collected before initiation of the rescue therapy.
  - Rescue therapy initiated on or before Day 28 during the RCP and treatment discontinuation will be analyzed using a treatment policy strategy. Subjects who discontinue treatment early will be asked to attend scheduled evaluations until the end of the RCP. The data collected after treatment discontinuation for reasons other than rescue therapy will be included in the analysis.
- Population-level summary: Mean difference between inebilizumab and placebo.

Supplementary analysis will be performed using a treatment policy strategy to address both intercurrent events of rescue therapy and treatment discontinuation (ie, including data collected after rescue or therapy and treatment discontinuation in the analysis).

The estimate of the treatment effect estimator for the overall study population will be based on a contrast from an MMRM model with covariates of treatment group, baseline antibody status (AChR-Ab+ or MuSK-Ab+), visit, the interaction of visit and treatment group, baseline steroid use, baseline QMG score, and baseline MG-ADL score.

The estimate of the treatment effect estimator for the AChR-Ab+ population or for the MuSK-Ab+ population will also be based on a contrast from an MMRM model but with covariates of treatment group, visit, the interaction of visit and treatment group, baseline steroid use, baseline QMG score, and baseline MG-ADL score.

Additional sensitivity analyses using MI approaches will also be conducted based on different missing data mechanism assumptions as suitable.

Details of the key secondary efficacy analyses will be included in the SAP.

#### 9.4.3 Analysis of Additional Secondary Efficacy Endpoints

The additional secondary efficacy endpoints include:

1. The proportion of subjects with  $\geq 3$ -point improvement in MG-ADL score at Week 26 and no use of rescue therapy between Day 28 and Week 26 in the overall study

- population, the AChR-Ab+ population, and the MuSK-Ab+ population, and at Week 52 and no use of rescue therapy between Day 28 and Week 52 in the AChR-Ab+ population.
2. Change from baseline in MG-ADL score at Week 52 in the AChR-Ab+ population.
  3. Change from baseline in QMG score at Week 52 in the AChR-Ab+ population.
  4. Change from baseline in MGC score at Week 26 and no use of rescue therapy between Day 28 and Week 26 in the overall study population, the AChR-Ab+ population, and the MuSK-Ab+ population, and at Week 52 and no use of rescue therapy between Day 28 and Week 52 in the AChR-Ab+ population.
  5. Change from baseline in MGQOL-15r score at Week 26 in the overall study population, AChR-Ab+, and MuSK-Ab+ and at Week 52 in AChR-Ab+ Week 26 in the overall study population, the AChR-Ab+ population, and the MuSK-Ab+ population and at Week 52 in the AChR-Ab+ population.
  6. PGIC score at Week 26 in the overall study population, the AChR-Ab+ population, and the MuSK-Ab+ population and at Week 52 in the AChR-Ab+ population.
  7. Time to first MG exacerbation by Week 26 in the overall study population, the AChR-Ab+ population, and the MuSK-Ab+ population and by Week 52 in the AChR-Ab+ population. Where an exacerbation is defined as one of the following:
    - Use of protocol-defined rescue therapy, or
    - Myasthenic crisis, defined as worsening of myasthenic weakness requiring intubation or noninvasive ventilation to avoid intubation, except when these measures are employed during routine postoperative management, or
    - Significant symptomatic worsening to a score of 3 or a 2-point increase from baseline on any one of the individual MG-ADL items other than double vision or eyelid droop.
  8. The safety and tolerability of inebilizumab as measured by the incidence of TEAEs, AESIs, and TESAEs. Laboratory measurements will also be evaluated as part of safety
  9. The proportion of subjects with steroid tapered to  $\leq 5$  mg/day at Week 26 for the overall study population, the AChR-Ab+ population, and the MuSK-Ab+ population and at Week 52 for the AChR-Ab+ population.
  10. The proportion of subjects in whom steroid dose was reduced by  $\geq 50\%$  by Week 26 for the overall study population, the AChR-Ab+ population, and the MuSK-Ab+ population and by Week 52 for AChR-Ab+ population.
  11. The proportion of subjects achieving minimal symptom expression, defined as MG-ADL = 0 or 1, at Week 26.
  12. Anti-drug antibody status and titer during the study in the overall study population, the AChR-Ab+ population, and the MuSK-Ab+ population.

#### 9.4.3.1 Analyses of the proportion

The primary estimand of the proportion of subjects is defined as follows:

- Population: Subjects in the FAS.
- Variable (endpoint): responder at the timepoint of interest (ie, a subject who achieved  $\geq 3$ -point improvement from baseline in MG-ADL score at Week 26 [or Week 52] and received no rescue therapy between Day 28 and Week 26 [or Week 52] will be considered as an MG-ADL responder).
- Intercurrent events:

- Rescue therapy: no rescue therapy after Day 28 during the RCP was part of the definition of the key secondary binary endpoints. A subject will be considered as a non-responder if rescue therapy was used between Day 28 and the timepoint of interest (Week 26 or Week 52).
- Rescue therapy initiated on or before Day 28 during the RCP and treatment discontinuation will be analyzed using a treatment policy strategy. Subjects who discontinue treatment early will be asked to attend scheduled evaluations until the end of the RCP. The data collected after treatment discontinuation for reasons other than rescue therapy will be included in the analysis.
- Population-level summary: difference of the inebilizumab vs placebo groups in the proportion of the responders regardless of treatment discontinuation.

Subjects will be considered as non-responders if they discontinue from the study before the timepoint of interest (Week 26 or Week 52).

The estimate of the treatment effect estimator will be evaluated using logistic regression with covariates of treatment group, baseline antibody status (AChR-Ab+ or MuSK-Ab+), baseline steroid use, baseline MG-ADL, baseline QMG score, and the corresponding baseline score. Sensitivity analyses may also be conducted for the proportions using a Cochran-Mantel-Haenszel test controlling for baseline antibody status (AChR-Ab+ or MuSK-Ab+), baseline steroid use, and baseline disease severity.

#### 9.4.3.2 Analyses of the changes from baseline

The primary estimand of the changes from baseline is the same as the one defined for the key secondary endpoints as mentioned in [Section 9.4.2](#). The estimate of the treatment effect estimator will also be based on a contrast from an MMRM approach with covariates of treatment group, baseline antibody status (AChR-Ab+ or MuSK-Ab+; this covariate is only needed for overall study population), visit, the interaction of visit and treatment group, baseline steroid use, baseline MG-ADL, baseline QMG score, and the corresponding baseline score (if the endpoint is not MG-ADL or QMG). For example, the estimate of the treatment effect estimator for change from baseline in MGC at Week 26 in the overall study population will be based on a contrast from an MMRM approach with covariates of treatment group, baseline antibody status, visit, the interaction of visit and treatment group, baseline steroid use, baseline MG-ADL, baseline QMG score, and baseline score MGC.

#### 9.4.3.3 Analyses for the time to first exacerbation

The primary estimand with a treatment policy strategy is defined by the following:

- Target population: Subjects in the FAS.
- Variable: Time in days from Day 1 (dosing) to the date of the first exacerbation by the timepoint of interest (Week 26 or Week 52).
- Intercurrent event: All data captured from Day 1 to the timepoint of interest will be used for analysis. Subjects who do not complete the timepoint of interest and who have not had an exacerbation between Day 1 and the timepoint of interest will be censored at the time of discontinuation or at the timepoint of interest, whichever is earlier.
- Population-level summary: Hazard ratio between inebilizumab versus placebo.

The hazard rate in the inebilizumab group will be compared to that in the placebo group using a Cox proportional hazard model with covariates of treatment group, baseline antibody status (AChR-Ab+ or MuSK-Ab+), baseline steroid use status, baseline QMG score, and baseline MG-ADL score.

Details of the analyses will be prespecified in the SAP.

#### 9.4.4 Analysis of Exploratory Efficacy Endpoints

#### 9.4.5 Multiplicity Control

The type I error will be controlled at 0.05 (2-sided) across the primary and the key secondary endpoints. A hierarchical approach will be applied for multiplicity control, and the testing strategy is proposed as follows:

- Step 1: Test the primary endpoint at a significance level of 0.05; if the p-value is  $< 0.05$ , then proceed to Step 2. Otherwise, no null hypothesis is rejected.
- Step 2: Test the key secondary endpoints at a significant level of 0.05 sequentially at alpha level 0.05 in the following order:
  - Change from baseline in QMG score at Week 26 in the overall study population.
  - Change from baseline in MG-ADL at Week 26 in the AChR-Ab+ population.
  - Change from baseline in QMG score at Week 26 in the AChR-Ab+ population.
  - Change from baseline in MG-ADL at Week 26 in the MuSK-Ab+ population.
  - Change from baseline in QMG score at Week 26 in the MuSK-Ab+ population.

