## 2.3 Study Hypotheses

**Primary Hypothesis:** Depletion of CD19+ B-cells with inebilizumab will improve outcomes in subjects with MG.

**Secondary Hypotheses:** In subjects with MG, treatment with inebilizumab will:

- Reduce the frequency of exacerbations
- Improve QOL
- Offer an acceptable safety and tolerability profile

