###### **Additional secondary endpoints:**

1. The proportion of subjects with  $\geq 3$ -point improvement in MG-ADL score at Week 26 and no use of rescue therapy [REDACTED] in the overall study population, the AChR-Ab+ population, and the MuSK-Ab+ population and at Week 52 and no use of rescue therapy [REDACTED] in the AChR-Ab+ population.
2. Change from baseline in MG-ADL score at Week 52 in the AChR-Ab+ population.
3. Change from baseline in QMG score at Week 52 in the AChR-Ab+ population.
4. Change from baseline in Myasthenia Gravis Composite (MGC) score at Week 26 in the overall study population, the AChR-Ab+ population, and the MuSK-Ab+ population and at Week 52 in the AChR-Ab+ population.
5. Change from baseline in Myasthenia Gravis Quality of Life-15 revised (MGQOL-15r) score at Week 26 in the overall study population, the AChR-Ab+ population, and the MuSK-Ab+ population and at Week 52 in the AChR-Ab+ population.

[figure not shown]
6. Patient Global Impression of Change (PGIC) score at Week 26 in the overall study population, the AChR-Ab+ population, and the MuSK-Ab+ population and at Week 52 in the AChR-Ab+ population.
7. Time to first MG exacerbation by Week 26 in the overall study population, the AChR-Ab+ population, and the MuSK-Ab+ population and by Week 52 in the AChR-Ab+ population. (Note: see [Section 9.4.3](#) for the definition of MG exacerbation.).
8. The safety and tolerability of inebilizumab as measured by the incidence of TEAEs, adverse events of special interest (AESIs), and TESAEs. Laboratory measurements will also be evaluated as part of safety.
9. The proportion of subjects with steroid tapered to  $\leq 5$  mg/day at Week 26 for the overall study population, the AChR-Ab+ population, and the MuSK-Ab+ population and at Week 52 for the AChR-Ab+ population.
10. The proportion of subjects in whom steroid dose was reduced by  $\geq 50\%$  by Week 26 for the overall study population, the AChR-Ab+ population, and the MuSK-Ab+ population and by Week 52 for the AChR-Ab+ population.
11. The proportion of subjects achieving minimal symptom expression, defined as MG-ADL = 0 or 1, at Week 26.
12. Anti-drug antibody status and titer during the study in the overall study population, the AChR-Ab+ population, and the MuSK-Ab+ population.

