3.1 General Considerations

All efficacy analyses described below apply to the RCP unless stated otherwise. The efficacy endpoints will be summarized at scheduled visits during RCP and OLP in the overall study population, AChR+-Ab+ population, and MuSK+-Ab + population, respectively. For subjects in the OLP, the efficacy may also be summarized over the combined RCP and OLP to characterize the durability of the treatment effect, if applicable.

[figure not shown]
The safety endpoints will be summarized for the RCP, OLP and combined study periods, respectively in the overall study population, AChR+-Ab+ population, and MuSK+-Ab + population, respectively.

Tabular summaries will be presented by treatment group. Categorical data will be summarized by the number and percentage of subjects in each category. [REDACTED]

All hypothesis testing will be reported using 2-sided tests. Unless otherwise stated, nominal p-values will be reported. P-values will be rounded to 4 decimal places. The 95% confidence interval (CI) will be reported as appropriate.

The absolute change from baseline is computed as (visit value – baseline value). Percent change from baseline is computed as (visit value – baseline value) / baseline value x 100%. If either a visit value or the baseline value is missing, the absolute change from baseline and the percent change from baseline will also be set to missing.

All statistical calculations will be primarily performed using SAS® System Version 9.4 or higher.

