3.4.6 Exploratory endpoints and Analyses

3.4.6.1 Exploratory Endpoints

3.4.6.2 Exploratory Endpoint Analyses

3.4.7 Subgroup Analyses

To explore the consistency of treatment effect, subgroup analyses will be performed on the FAS for the primary and the key secondary endpoints in the following subgroups as appropriate.

[REDACTED]

These analyses are to be considered as exploratory and will be performed on the FAS. Interaction tests would be conducted to evaluate the consistency of the treatment effect among the different categories of each subgroup variable.

[REDACTED]

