3.8 Multiplicity Adjustment

The type I error will be controlled across the primary and the key secondary endpoints at 0.05 (2-sided). A hierarchical approach will be used to control for multiplicity and the testing strategy is proposed as follows:

- Step 1: Test the primary endpoint at a significance level (2-sided) of 0.05; if the p-value is less than 0.05, then proceed to Step 2. Otherwise, no null hypothesis is rejected in the overall population.
- Step 2: Test the key secondary endpoints at a significance level (2-sided) of 0.05 sequentially following the order below:
 - Change from baseline in QMG score at Week 26 in the overall study population.

- Change from baseline in MG-ADL score at Week 26 in the AChR-Ab+ population.
- Change from baseline in QMG score at Week 26 in the AChR-Ab+ population.
- Change from baseline in MG-ADL score at Week 26 in the MuSK-Ab+ population.
- Change from baseline in QMG score at Week 26 in the MuSK-Ab+ population.

4. Planned Analysis

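### The stated secondary hypotheses on exacerbations and quality of life have no type-I-controlled test, although two tests could be appended to the fixed sequence at no cost in alpha

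*Protocol*

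**What the plan says.** Protocol 2.3 lists the secondary hypotheses. The first is "Reduce the frequency of exacerbations", the second is improved quality of life, and the third is acceptable safety and tolerability. Protocol 3.2.1 makes the first two its secondary objectives 1 and 2.

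The endpoints that serve them are additional secondary endpoints (the SAP calls this tier other secondary):

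- Exacerbations (Protocol 9.4.3): "Time to first MG exacerbation by Week 26 in the overall study population, the AChR-Ab+ population, and the MuSK-Ab+ population", plus AChR-Ab+ by Week 52. The analysis is a Cox model (Protocol 9.4.3.3).
- Quality of life (Protocol 3.2.2): "Change from baseline in Myasthenia Gravis Quality of Life-15 revised (MGQOL-15r) score at Week 26 in the overall study population", plus each antibody population at Week 26 and AChR-Ab+ at Week 52. The analysis is an MMRM (Protocol 9.4.3.2).

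On multiplicity, Protocol 9.4.5 says: "The type I error will be controlled at 0.05 (2-sided) across the primary and the key secondary endpoints". SAP 3.8 sets the same scope. The order in both documents is:

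1. MG-ADL, overall (primary)
2. QMG, overall
3. MG-ADL, AChR-Ab+
4. QMG, AChR-Ab+
5. MG-ADL, MuSK-Ab+
6. QMG, MuSK-Ab+

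All six are changes from baseline at Week 26. For p-values in general, SAP 3.1 says: "Unless otherwise stated, nominal p-values will be reported".

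**The concern.** The protocol commits in advance to two efficacy hypotheses beyond MG-ADL and QMG, collects the data for them in both populations, and specifies an estimand and a model for each. The testing plan then stops before reaching either. If inebilizumab does delay exacerbations or improve quality of life, the trial can report a nominal p-value but cannot claim the result with familywise error control, however strong it is. The sequence could have been extended to include these endpoints without weakening any test already in it.

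**Working it through.** **Inputs.**
- Two-sided alpha 0.05 and the six-step order: Protocol 9.4.5, SAP 3.8.
- 188 AChR-Ab+ and 42 MuSK-Ab+ subjects, 1:1, so 115, 94 and 21 per arm (overall, AChR-Ab+, MuSK-Ab+); MG-ADL difference 2, SD 4: Protocol 9.2, SAP 2.3.
- Correlation between the exacerbation and MGQOL-15r test statistics: not given. Assumed, from 0 to 0.9.

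**Step 1: the plan's own figures.** The noncentrality is d / (SD × √(2/n)), and power comes from the noncentral t at two-sided 0.05.
- Overall: 2 / (4 × √(2/115)) = 3.79, power 96.5%. The plan says more than 95%.
- AChR-Ab+: 2 / (4 × √(2/94)) = 3.43, power 92.6%. The plan says at least 90%.
- MuSK-Ab+ minimum detectable difference: t(0.975, 40) × 4 × √(2/21) = 2.021 × 1.234 = 2.49. The plan says 2.5.

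All three reproduce.

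**Step 2: the existing alpha control.** In a fixed sequence, a false rejection requires rejecting the first true null in the order. That null is tested at 0.05, so familywise error is at most 0.05 whatever the number of steps. The six-step plan is valid.

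**Step 3: two tests left outside.** If both nulls are true and each is judged at 0.05, the chance of at least one false positive under independence is 1 − 0.95² = 0.0975. With equicorrelated normal statistics (200,000 draws):

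| Correlation | 0 | 0.3 | 0.5 | 0.7 | 0.9 |
|---|---|---|---|---|---|
| Chance of at least one | 0.097 | 0.095 | 0.090 | 0.084 | 0.070 |

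The range is about 7% to 10%, or 1.4 to 1.95 times 0.05.

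**Step 4: two tests appended.** The argument in step 2 applies unchanged to eight steps. Familywise error stays at 0.05, and the first six tests keep their order, level and power.

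**Step 5: how often the new tests would be reached.** All six earlier tests must succeed, so the chance of reaching the seventh cannot exceed the power of the weakest. For MuSK-Ab+ MG-ADL with 21 per arm and SD 4:
- Difference 2: noncentrality 2 / 1.234 = 1.62, power 35%.
- Difference 2.5: noncentrality 2.5 / 1.234 = 2.03, power 51%.

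These are upper limits, because MuSK-Ab+ QMG must also succeed. The documents give no QMG difference or SD, so the limit cannot be tightened. They also give no exacerbation rate, hazard ratio or MGQOL-15r SD, so power for the two new tests cannot be computed.

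**The case against.** The strongest reply is that nothing in the plan is wrong. It has a controlled tier and an uncontrolled tier, SAP 3.1 calls p-values nominal unless otherwise stated, and no confirmatory claim is made for these endpoints. Protocol 2.3 can be read as a list of expectations, since its third item, safety, is summarised without a formal test. This stands as far as error control goes. It does not explain why two pre-stated efficacy hypotheses go without a controlled test when adding one for each takes nothing from the rest.

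A reader might go further and count every additional secondary comparison. Protocol 9.4.3 gives 4 + 1 + 1 + 4 + 4 + 4 + 4 + 4 + 4 + 1 = 31, and one might conclude that a false positive somewhere is likely. The documents do not support that as a finding about this trial. No 5% decision threshold is stated for these endpoints. The figure requires all 31 nulls to be true. It also runs from 0.80 at zero correlation to 0.17 at 0.9, with no correlation given, and the comparisons overlap heavily: 188 of the 230 subjects in the overall population are AChR-Ab+.

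A reader might also infer that the plan leaves these p-values open to confirmatory reading because only the subgroup analyses are labelled: "These analyses are to be considered as exploratory and will be performed on the FAS". That absence can be seen only in the readable text, since SAP 3.4.5.2 is partly redacted, and calling the p-values nominal already conveys most of what such a label would say.

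The last objection is that a place at the end of the sequence will often not be reached. That is correct, and step 5 gives its size.

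**Conclusion.** The point holds as an optional improvement. Neither the exacerbation nor the quality-of-life hypothesis has a type-I-controlled test, and both could have one at no cost in alpha or in power for the existing tests. The present alpha control is valid, and the plan does not claim confirmation for these endpoints.

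The size is modest. The two tests left outside carry a joint false-positive chance of about 7% to 10%, assuming both nulls are true, each is read at 0.05, and the correlation lies between 0.9 and 0. The benefit is capped as well: the appended tests are reached at most about 35% of the time at a MuSK-Ab+ MG-ADL difference of 2, or 51% at 2.5, under the plan's SD of 4.

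**What to change.** Before the database lock for the primary analysis and the unblinding that follows it, add to the end of the order in Protocol 9.4.5 and SAP 3.8, after the fifth key secondary endpoint:

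- Key secondary 6: time to first MG exacerbation by Week 26, overall population.
- Key secondary 7: change from baseline in MGQOL-15r at Week 26, overall population.

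Test each at two-sided 0.05 only if all earlier tests succeed. State alongside that both MuSK-Ab+ tests must succeed first, with the 35% and 51% figures.

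The cost is an amendment to the multiplicity section of both documents, with the usual approvals. No new data are needed: MGQOL-15r is already scheduled from Day 1 to Week 26 in both populations (Protocol Tables 3 and 4), and the exacerbation definition and both models already exist. Protocol 9.1 allows final SAP amendments up to database lock.

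Placing the two tests ahead of the MuSK-Ab+ steps would raise the cap to about 93%, set by AChR-Ab+ MG-ADL, and would still hold 0.05. It would also make the MuSK-Ab+ claims depend on the new tests, so it is a trade-off for the sponsor to justify and not the free change recommended here.
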